**Post-Dose 3**

**Table 67:** Number and Percentage of Subjects Experiencing Solicited Events by Symptom, Severity, and Day Post Dosing – Cohort 2 ANDV DNA 2mg - Post Dose 3

**Table 68:** Number and Percentage of Subjects Experiencing Solicited Events by Symptom, Severity, and Day Post Dosing – Cohort 4 ANDV DNA 4mg - Post Dose 3

**Table 69:** Number and Percentage of Subjects Experiencing Solicited Events by Symptom, Severity, and Day Post Dosing – All Placebo Including Cohorts 1 and 3 - Post Dose 3

**Table 70:** Number and Percentage of Subjects Experiencing Solicited Events by Symptom, Severity, and Day Post Dosing – All Subjects - Post Dose 3

**Post-Dose 4**

**Table 71:** Number and Percentage of Subjects Experiencing Solicited Events by Symptom, Severity, and Day Post Dosing – Cohorts 1 and 2 ANDV DNA 2mg - Post Dose 4

**Table 72:** Number and Percentage of Subjects Experiencing Solicited Events by Symptom, Severity, and Day Post Dosing – Cohorts 3 and 4 ANDV DNA 4mg - Post Dose 4

**Table 73:** Number and Percentage of Subjects Experiencing Solicited Events by Symptom, Severity, and Day Post Dosing – All Placebo - Post Dose 4

**Table 74:** Number and Percentage of Subjects Experiencing Solicited Events by Symptom, Severity, and Day Post Dosing – All Subjects - Post Dose 4

**Post-Any Dose**

**Table 75:** Number and Percentage of Subjects Experiencing Solicited Events by Symptom, Maximum Severity, and Day Post Dosing – Cohort 1 ANDV DNA 2mg (3 Doses) - Post Any Dose

**Table 76:** Number and Percentage of Subjects Experiencing Solicited Events by Symptom, Maximum Severity, and Day Post Dosing – Cohort 2 ANDV DNA 2mg (4 Doses) - Post Any Dose

**Table 77:** Number and Percentage of Subjects Experiencing Solicited Events by Symptom, Maximum Severity, and Day Post Dosing – Cohort 3 ANDV DNA 4mg (3 Doses) - Post Any Dose

**Table 78:** Number and Percentage of Subjects Experiencing Solicited Events by Symptom, Maximum Severity, and Day Post Dosing – Cohort 4 ANDV DNA 4mg (4 Doses) - Post Any Dose

**Table 79:** Number and Percentage of Subjects Experiencing Solicited Events by Symptom, Maximum Severity, and Day Post Dosing – All Placebo - Post Any Dose

**Table 80:** Number and Percentage of Subjects Experiencing Solicited Events by Symptom, Maximum Severity, and Day Post Dosing – All Subjects - Post Any Dose

### 14.3.1.2 Unsolicited Adverse Events

**Table 81: Frequency and Proportion of Subjects with Unsolicited Adverse Events by MedDRA System Organ Class, Preferred Term, and Vaccination Group – Post-Dose 1**

	Cohorts 1 + 2 ANDV DNA 2 mg (N=X)		Cohorts 3 + 4 ANDV DNA 4 mg (N=X)		All Placebo (N=X)		All Subjects (N=X)	
	n (%)	95% CI	n (%)	95% CI	n (%)	95% CI	n (%)	95% CI
Any SOC								
Any PT	x (x.x)	x.x, x.x	x (x.x)	x.x, x.x	x (x.x)	x.x, x.x	x (x.x)	x.x, x.x
[SOC 1]								
Any PT								
[PT 1]								
[PT 2]								
Etc..								
[Etc.]								

Note: N=Number of subjects in the Safety Population who received the specified dose; n=Number of subjects experiencing an AE within the SOC and PT combination.

95% CI = Exact Clopper-Pearson confidence interval.

Includes any mild or greater AEs reported post-dose 1 and prior to dose 2, or through 28 days post dose 1 if dose 2 not received.

Table with similar format:

**Table 82: Frequency and Proportion of Subjects with Unsolicited Adverse Events by MedDRA System Organ Class, Preferred Term, and Vaccination Group – Post-Dose 2**

**Table 83: Frequency and Proportion of Subjects with Unsolicited Adverse Events by MedDRA System Organ Class and Preferred Term and Vaccination Group – Post-Dose 3**

	Cohort 1 ANDV DNA 2 mg (N=X)		Cohort 2 ANDV DNA 2 mg (N=X)		Cohort 3 ANDV DNA 4 mg (N=X)		Cohort 4 ANDV DNA 4 mg (N=X)		All Placebo (N=X)		All Subjects (N=X)	
	n (%)	95% CI	n (%)	95% CI	n (%)	95% CI						
Any SOC												
Any PT	x (x.x)	x.x, x.x	x (x.x)	x.x, x.x	x (x.x)	x.x, x.x						
[SOC 1]												
Any PT												
[PT 1]												
[PT 2]												
Etc..												
[Etc.]												

Note: N=Number of subjects in the Safety Population who received the specified dose; n=Number of subjects experiencing an AE within the SOC and PT combination.

95% CI = Exact Clopper-Pearson confidence interval.

Includes any mild or greater AEs reported post-dose 3 and prior to dose 4, or through 28 days post dose 3 if dose 4 not received.

Tables with similar format:

**Table 84: Frequency and Proportion of Subjects with Unsolicited Adverse Events by MedDRA System Organ Class and Preferred Term and Vaccination Group – Post-Dose 4****Table 85: Frequency and Proportion of Subjects with Unsolicited Adverse Events by MedDRA System Organ Class and Preferred Term and Vaccination Group – Through 28 Days Post-Final Dose Received**

**Table 86: Frequency of Unsolicited Adverse Events by MedDRA System Organ Class and Preferred Term and Vaccination Group – Post Dose 1 and Post-Dose 2**

	Cohorts 1 + 2 ANDV DNA 2 mg (N=X)			Cohorts 3 + 4 ANDV DNA 4 mg (N=X)			All Placebo (N=X)			All Subjects (N=X)		
	Dose 1 n	Dose 2 n	Total n	Dose 1 n	Dose 2 n	Total n	Dose 1 n	Dose 2 n	Total n	Dose 1 n	Dose 2 n	Total n
Any SOC												
Any PT	x	x	x	x	x	x	x	x	x	x	x	x
[SOC 1]												
Any PT												
[PT 1]												
[PT 2]												
Etc..												
[Etc.]												

Note: N=Number of subjects in the Safety Population who received the specified dose; n=Total number of AEs within the SOC and PT combination.

Total = AEs reported post dose 1 or post-dose 2.

Includes all mild or greater AEs reported at any time post-each dose, or through 28 days post dose if subsequent dose not received.

**Table 87: Frequency of Unsolicited Adverse Events, by MedDRA System Organ Class and Preferred Term and Vaccination Group – Post Dose 3, Post-Dose 4, and Post-Any Dose**

	Cohort 1 ANDV DNA 2 mg (N=X)			Cohort 2 ANDV DNA 2 mg (N=X)			Cohort 3 ANDV DNA 4 mg (N=X)			Cohort 4 ANDV DNA 4 mg (N=X)			All Placebo (N=X)			All Subjects (N=X)		
	Dose 3	Dose 4	Any Time	Dose 3	Dose 4	Any Time	Dose 3	Dose 4	Any Time	Dose 3	Dose 4	Any Time	Dose 3	Dose 4	Any Time	Dose 3	Dose 4	Any Time
Any SOC																		
Any PT																		
[SOC 1]																		
Any PT																		
[PT 1]																		
[PT 2]																		
Etc..																		
[Etc.]																		

Note: N=Number of subjects in the Safety Population who received the specified dose; n=Total number of AEs within the SOC and PT combination.

Includes all mild or greater AEs reported at any time post-each dose, or through 28 days post dose if subsequent dose not received.

Any Time = number of AEs reported at any time post-dose 1.

**Table 88: Frequency and Percent of Subjects with Unsolicited Adverse Events by MedDRA System Organ Class and Preferred Term, Maximum Severity, and Relationship – ANDV DNA 2 mg - Post-Doses 1 and 2**

MedDRA System Organ Class	Preferred Term	Severity	Events Related to IP		Events Not Related to IP		Any Event		
			n	%	n	%	n	%	
Post Dose 1 (N = X)									
Any SOC	Any PT	Any Severity	x	xx	x	xx	x	xx	
		Mild							
		Moderate							
		Severe							
SOC 1	PT 1	Any Severity							
		Mild							
		Moderate							
		Severe							
	PT 2	Any Severity							
		Mild							
		Moderate							
		Severe							
Repeat for									
Post Dose 2 (N = X)									
Post Dose 1 or 2 (N = X)									

Note: N=Number of subjects in the Safety Population; n=Number of subjects experiencing an AE within the SOC and PT combination. Severity is the maximum severity reported post dosing for each subject for each day.

Tables with similar format:

**Table 89: Frequency and Percent of Subjects with Unsolicited Adverse Events by MedDRA System Organ Class and Preferred Term, Maximum Severity, and Relationship – ANDV DNA 4 mg - Post-Doses 1 and 2**

**Table 90: Frequency and Percent of Subjects with Unsolicited Adverse Events by MedDRA System Organ Class and Preferred Term, Maximum Severity, and Relationship – Placebo - Post-Doses 1 and 2**

**Table 91: Frequency and Percent of Subjects with Unsolicited Adverse Events by MedDRA System Organ Class and Preferred Term, Maximum Severity, and Relationship – ANDV DNA 2 mg (3 Doses) - Post-Dose 3 and 4, and At Any Time**

MedDRA System Organ Class	Preferred Term	Severity	Events Related to IP		Events Not Related to IP		Any Event		
			n	%	n	%	n	%	
Post Dose 3 (N = X)									
Any SOC	Any PT	Any Severity	x	xx	x	xx	x	xx	
		Mild							
		Moderate							
		Severe							
SOC 1	PT 1	Any Severity							
		Mild							
		Moderate							
		Severe							
	PT 2	Any Severity							
		Mild							
		Moderate							
		Severe							
Repeat for									
Post Dose 4 (N = X)									
Any Time (N = X)									

Note: N=Number of subjects in the Safety Population; n=Number of subjects experiencing an AE within the SOC and PT combination. Severity is the maximum severity reported post dosing for each subject for each day.

 Any AE reported post-dose 1.

Tables with similar format:

**Table 92: Frequency and Percent of Subjects with Unsolicited Adverse Events by MedDRA System Organ Class and Preferred Term, Maximum Severity, and Relationship – ANDV DNA 2 mg (4 Doses) - Post-Dose 3 and 4, and At Any Time**

**Table 93: Frequency and Percent of Subjects with Unsolicited Adverse Events by MedDRA System Organ Class and Preferred Term, Maximum Severity, and Relationship – ANDV DNA 4 mg (3 Doses) - Post-Dose 3 and 4, and At Any Time**

**Table 94: Frequency and Percent of Subjects with Unsolicited Adverse Events by MedDRA System Organ Class and Preferred Term, Maximum Severity, and Relationship – ANDV DNA 4 mg (4 Doses) - Post-Dose 3 and 4, and At Any Time**

**Table 95: Frequency and Percent of Subjects with Unsolicited Adverse Events by MedDRA System Organ Class and Preferred Term, Maximum Severity, and Relationship – Placebo - Post-Dose 3 and 4, and At Any Time**

**Table 96: Frequency and Percent of Subjects with Unsolicited Adverse Events by MedDRA System Organ Class and Preferred Term, Maximum Severity, and Relationship – All Subjects**

MedDRA System Organ Class	Preferred Term	Severity	Events Related to IP		Events Not Related to IP		Any Event		
			n	%	n	%	n	%	
Post Dose 1 (N = X)									
Any SOC	Any PT	Any Severity	X	XX	X	XX	X	XX	
		Mild							
		Moderate							
		Severe							
SOC 1	PT 1	Any Severity							
		Mild							
		Moderate							
		Severe							
	PT 2	Any Severity							
		Mild							
		Moderate							
		Severe							
Repeat for									
Post Dose 2 (N = X)									
Post Dose 3 (N = X)									
Post Dose 4 (N = X)									
Any Time (N = X)									

Note: N=Number of subjects in the Safety Population; n=Number of subjects experiencing an AE within the SOC and PT combination. Severity is the maximum severity reported post dosing for each subject for each day.

 Any AE reported post-dose 1.

AEs related to IP

Same format as Table 81:

**Table 97: Frequency and Percent of Subjects with Unsolicited Adverse Events Related to IP by MedDRA System Organ Class, Preferred Term, and Vaccination Group – Post-Dose 1**

**Table 98: Frequency and Percent of Subjects with Unsolicited Adverse Events Related to IP by MedDRA System Organ Class, Preferred Term, and Vaccination Group – Post-Dose 2**

Same format as Table 83:

**Table 99: Frequency and Percent of Subjects with Unsolicited Adverse Events Related to IP by MedDRA System Organ Class, Preferred Term, and Vaccination Group – Post-Dose 3**

**Table 100: Frequency and Percent of Subjects with Unsolicited Adverse Events Related to IP by MedDRA System Organ Class, Preferred Term, and Vaccination Group – Post-Dose 4**

**Table 101: Frequency and Percent of Subjects with Unsolicited Adverse Events Related to IP by MedDRA System Organ Class, Preferred Term, and Vaccination Group – Any Time**

Same format as Table 86:

**Table 102: Frequency of Unsolicited Adverse Events Related to IP by MedDRA System Organ Class and Preferred Term and Vaccination Group – Post Dose 1 and Post-Dose 2**

Same format as Table 87:

**Table 103: Frequency of Unsolicited Adverse Events Related to IP by MedDRA System Organ Class and Preferred Term and Vaccination Group – Post Dose 3, Post-Dose 4 and Any Time**

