3.2 Study Outcome Measures

3.2.1 Primary Outcome Measures

- Occurrence of vaccine-related Serious Adverse Events (SAEs) through approximately 6 months post last vaccination.
- Occurrence of vaccine-related unsolicited Adverse Events (AEs) through 28 days post last vaccination.
- Occurrence of Serious Adverse Events (SAEs) through approximately 6 months post last vaccination.
- Occurrence of unsolicited Adverse Events (AEs) through 28 days post last vaccination.
- Occurrence of solicited local and systemic AEs through 7 days after each study vaccination.
- Occurrence of clinical safety laboratory AEs through 7 days after each study vaccination.

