### 9.3.2. Unsolicited Adverse Events

The proportion of subjects reporting at least one unsolicited adverse event will be summarized by MedDRA system organ class and preferred term for each vaccination and over all vaccinations. Denominators for percentages are the number of subjects in the Safety population who received the vaccination being summarized.

Unsolicited adverse events by subject will be presented in [Listing 11](#).

The following summaries for unsolicited adverse events will be presented by MedDRA system organ class, preferred term, dose and vaccination group:

- Incidence and 95% CI of unsolicited adverse events after each dose and any time during the study will be summarized in [Table 81](#), [Table 82](#), [Table 83](#), [Table 84](#), and [Table 85](#);

- The total frequency of unsolicited adverse events after each dose and any time during the study will be summarized in [Table 86](#) and [Table 87](#);
- Summary of severity and relationship to study product after dose 1 and dose 2 ([Table 88](#), [Table 89](#), and [Table 90](#));
- Summary of severity and relationship to study product after dose 3 and dose 4 and at any time ([Table 91](#), [Table 92](#), [Table 93](#), [Table 94](#), [Table 95](#), and [Table 96](#));
- Incidence and 95% CI of unsolicited adverse events related to IP, after each dose and any time during the study will be summarized in [Table 97](#), [Table 98](#), [Table 99](#), [Table 100](#), and [Table 101](#);
- The total frequency of unsolicited adverse events related to IP, after each dose and any time during the study will be summarized in [Table 102](#) and [Table 103](#);
- Subject listing of SAEs ([Table 104](#));
- Bar chart of the total frequency of non-serious related unsolicited adverse events by severity and MedDRA system organ class ([Figure 43](#), [Figure 44](#), [Figure 45](#), [Figure 46](#), and [Figure 47](#));
- Bar chart of the incidence of non-serious related unsolicited adverse events by maximum severity and MedDRA system organ class ([Figure 48](#), [Figure 49](#), [Figure 50](#), [Figure 51](#), and [Figure 52](#));

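### The SAP's by-dose displays of unsolicited AEs have no common window: Post-Dose 3 runs a planned 112 to 117 days, against about 28 to 30 days after each other dose

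*SAP*

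**What the plan says.** SAP 9.3.2 plans incidence with 95% confidence intervals for unsolicited AEs after each dose. On denominators it says: "Denominators for percentages are the number of subjects in the Safety population who received the vaccination being summarized".

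The windows are set in the table footnotes of SAP Appendix 1, section 14.3.1.2:

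- Table 83 (Post-Dose 3) counts "AEs reported post-dose 3 and prior to dose 4, or through 28 days post dose 3 if dose 4 not received". Table 81 has the matching rule for dose 1, and Table 82 takes its format.
- Tables 86 and 87 say: "Includes all mild or greater AEs reported at any time post-each dose, or through 28 days post dose if subsequent dose not received". Table 87 gives each cohort adjacent Dose 3 and Dose 4 columns.
- The related-AE tables inherit these layouts: Table 99 is headed "Same format as Table 83" and Table 103 "Same format as Table 87".
- Table 85 runs "Through 28 Days Post-Final Dose Received". This follows the Protocol 3.2.1 outcome, "Occurrence of unsolicited Adverse Events (AEs) through 28 days post last vaccination".
- The any-time rows of Tables 91 to 96 take "Any AE reported post-dose 1". The Post-Dose 3 blocks of the same tables state no window.

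Doses are due on Days 1, 29 (+2), 57 (+2) and 169 (+5) (SAP 4.3.5). AE collection does not pause in the long gap: Protocol 7.6 has AEs recorded at Day 141.

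**The concern.** A rule that runs to the next dose gives equal windows only if the doses are equally spaced, and dose 4 comes about four months after dose 3. The denominator is a head count of those dosed. No by-dose table gives a rate, a common cut-off or the window length. Even if the vaccine had no effect, a longer window with continued collection would be expected to put more subjects and more events under dose 3.

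The contrast is least helpful in Cohorts 1 and 3, where dose 3 is placebo and dose 4 is vaccine (SAP Table 1). There the longer window belongs to placebo, so the unequal lengths can mask an excess after the vaccine dose.

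A second effect comes from the fallback. A subject who misses dose 4 contributes only 28 days to Table 83, in the same denominator as subjects followed for 112 to 117 days. A late severe AE can itself be the reason dose 4 is missed.

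**Working it through.** **Interval from dose 3 to dose 4.** The Schedule of Events (Protocol Appendix A) puts the dose 4 visit at Day 113, +5, counted from Vaccine 3. The nominal days reproduce this: 169 − 57 + 1 = 113. The vaccination day is Day 1, so the elapsed time is 113 − 1 = 112 days, or 112 + 5 = 117 with the allowance.

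**Window by dose.** Visits are anchored to the preceding vaccination (Protocol 7.3 and Appendix A). AE visits are from Protocol 7.3 to 7.6 and Appendix A.

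| Display | Window ends | Planned days | Scheduled AE visits |
|---|---|---|---|
| Post-Dose 1 | dose 2 | 28–30 | Days 8, 29 |
| Post-Dose 2 | dose 3 | 28–30 | Days 36, 57 |
| Post-Dose 3 | dose 4 | 112–117 | Days 64, 85, 141, 169 |
| Post-Dose 4 | 28 days (no later dose) | about 28 | Days 176, 197 |

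Ratios of length: 112/30 = 3.73; 117/30 = 3.90; 112/28 = 4.00; 117/28 = 4.18.

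If the allowances are instead read from Vaccine 1, dose 2 to dose 3 is 57 − 31 = 26 to 59 − 29 = 30 days, and dose 3 to dose 4 is 169 − 59 = 110 to 174 − 57 = 117 days. The conclusion is the same.

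**What this could do to a proportion (assumed rates only).** Let p be the 28-day incidence with no vaccine effect. If AEs are recorded at a constant rate, the dose 3 proportion is 1 − (1 − p)^(d/28) with d = 112 to 117. If recording follows the number of visits (4 against 2), it is 1 − (1 − p)².

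| Assumed p | Constant rate | By visits |
|---|---|---|
| 5% | 18.5–19.3% | 9.8% |
| 10% | 34.4–35.6% | 19.0% |
| 20% | 59.0–60.6% | 36.0% |

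Neither column is a bound. The memory aid covers only 7 days after each dose (SAP 4.4.1), so the unaided Day 141 and Day 169 visits may yield less than Day 64, and the true excess could fall below the visit figures. Neither model applies to product-related AEs (Tables 99 and 103).

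**Mixed follow-up.** For a cohort of 10 with k subjects missing dose 4, at p = 10% and a constant rate, the expected Table 83 proportion is ((10 − k) × 0.344 + k × 0.10)/10. This gives 34.4%, 32.0% and 29.5% for k = 0, 1 and 2, a small effect.

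**A late Grade 3 AE traced through the tables.**

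1. It starts more than 28 days after dose 3 and is still Grade 3 when dose 4 is due. SAP 4.2.3 then withholds dose 4.
2. With dose 4 not received, the Table 83 footnote falls back to 28 days, and the event is left out.
3. Dose 3 is now the final dose, so Table 85 also ends before the onset.
4. An AE with the same onset that has dropped to Grade 1 or 2, in a subject who then receives dose 4, is counted in Table 83.
5. The omitted event still appears in Table 47 (subjects with a Grade 3 unsolicited AE), in Table 105 (or Table 104 if serious), in the any-time rows and in Listing 11.

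**The case against.** The strongest reply is that the rule is stated, applied uniformly, and easy to decode from the published dosing days. Assigning an AE to the most recent dose is a coherent convention. The primary objective is safety by dosage cohort and treatment arm, not by dose number, and no hypothesis is tested. All columns within Table 83 share one planned window. Tables 81 and 82 pool cohorts by dosage while Table 83 separates them, so only the placebo and all-subjects columns line up across those tables.

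Much of this stands: the comparisons between groups that serve the objective are not distorted. It does not rescue the reading across doses, which the SAP invites by planning incidence after each dose, setting Dose 3 beside Dose 4 in Table 87, and stacking doses in Tables 91 to 96. Being able to work out that the windows differ does not make the figures comparable.

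A reader might also infer more than the documents support:

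- *Dose 3 will show about four times the AEs.* The ratio of 3.7 to 4.2 is of window lengths. It equals a ratio of expected AE counts only if the recorded rate is constant, and it does not carry over to related AEs.
- *Table 87 states the Table 83 rule.* Its footnote never mentions stopping at dose 4; that is inferred from its separate columns. A literal reading would only lengthen the dose 3 window.
- *The tables hide a severe late event.* It is missing from Tables 83 and 85 but appears in the other displays traced above. Its absence from Table 85 follows the protocol outcome period and is not a SAP error.
- *Figures 45 and 50 use the long window.* Their mock-ups are not reproduced in the text available, so this cannot be checked.

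**Conclusion.** The point holds for the by-dose displays. A stated rule makes the planned dose 3 window 112 to 117 days in Table 83 and, by format, Table 99; Tables 87 and 103 imply the same. The other doses have about 28 to 30 days, and nothing in the displays adjusts for the difference. A dose given outside its planned window would change these lengths.

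The size of the resulting excess is unknown. The illustrative percentages rest on assumed background rates and assumed recording patterns. How often a late Grade 3 AE would both prevent dose 4 and drop out of Table 83 is also unknown. The consequence is limited to descriptive displays: the protocol outcome, the between-group comparisons within Table 83 and the any-time summaries stand as planned. The change is still worth making before the tables are produced, because it is cheap and removes a misleading contrast without losing an event.

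**What to change.** - In Tables 83, 87, 99 and 103, define Post-Dose 3 as onset from dose 3 through 28 days after it, or to dose 4 if earlier. State the same window in the Post-Dose 3 blocks of Tables 91 to 96 and apply it to Figures 45 and 50.
- Add a separate row (a column where doses are columns) for onsets more than 28 days after dose 3 and before dose 4, with subjects who received dose 4 as the denominator.
- List separately any recorded late onsets in subjects who did not receive dose 4, and give the number of such subjects. Do not pool them into the late row: non-serious AE collection formally ends about 28 days after the last vaccination (Protocol 9.1), so their late follow-up may be incomplete.
- Leave the dose 1 and dose 2 rule as written, so that no Day 29 or Day 30 onset is lost; the remaining difference of up to 2 days is minor. Leave Table 85 and the any-time tables unchanged.

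The cost is a few footnotes, one derivation and one added row. Listing 11 already carries days since the associated dose, so no new data are needed. The small downside is that late onsets leave the dose 3 row and must be read in their own.

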5.4.3 Discontinuation of Study Product

There are several reasons why a study subject may be prevented from receiving the second, third or fourth vaccination. If a subject's study vaccine must be discontinued before the end of the vaccination schedule, this will not result in automatic withdrawal of the subject from the study.

Subjects who discontinue study vaccine will be encouraged to remain in this trial for the following follow-up assessments:

- Safety assessments: Venous blood sample at approximately 7 days after the last study vaccination. Subjects will be asked to complete the remaining study assessments per Appendix A, Schedule of Events which may be conducted by phone call/electronic communication (e.g., email, text message) rather than in person continuing through approximately 6 months after the last study vaccination.
- Immunogenicity assessments: Venous blood sample at Day 29, 85 and approximately 6 months after the last study vaccination See the protocol-specific Manual of Procedures (MOP) for alternate follow-up requirements.

Follow-up study vaccinations (2nd, 3rd and/or 4th dose) will not be administered to a subject if any of the following criteria are met:

- Pregnancy
- Receipt of disallowed licensed vaccine, experimental product or medication (see Section 5.2)
- New onset of illness or condition that meets the Exclusion Criteria (see Section 5.2)
- Medical condition or medication change for which continued participation, in the opinion of the site principal investigator or appropriate sub-investigator, would pose a risk to the subject or would likely confound interpretation of the results. Note: Medication changes subsequent to the first study vaccination are not exclusionary for receipt of the follow-up study vaccination provided there was no deterioration in the subject's chronic medical condition that necessitated a medication change, and there is no additional risk to the subject or interference with the evaluation of responses to study vaccination.
- Presence of signs or symptoms that could confound or confuse assessment of study vaccine reactogenicity.
- Any laryngospasm, bronchospasm, or anaphylaxis within 1 day after administration of study product that is considered related to study product.
- Any generalized urticaria after administration of study product that is considered related to study product.
- Serious adverse event related to the study vaccination.

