7.6 Follow-up Visits

Day 141 & 253

Follow-up visits are scheduled in reference to study vaccination date as indicated for each visit window, see Appendix A, SOE. All Treatment Arms will return on D141 (V8) and D253 (V12).

- Interim medical history will be obtained by interview of subjects to ensure continued eligibility. Any changes since the previous clinic visit or contact will be noted at each clinic visit.
- All concomitant medications (including solicitation for receipt of any non-study vaccines) will be recorded on the appropriate data collection form at the Day 141 clinic visit. Any new concomitant medications taken since the previous clinic visit or contact will be reviewed with subjects and assessed for continued eligibility.
- A targeted physical examination may be performed, if indicated based on review of complete medical history and any updates obtained by interview of subjects, by a study clinician listed on the Form FDA 1572.
- Venous blood will be collected for ANDV PsVNA antibody assays at Day 253.
- All AEs will be collected and recorded on the appropriate data collection form at day 141.
- SAEs will be collected and recorded on the appropriate data collection form at each clinic visit.

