## 9.3. Adverse Events

When calculating the incidence of adverse events (i.e., on a per subject basis), each subject will only be counted once and any repetitions of adverse events within a subject will be ignored; the denominator will be the number of subjects in the Safety population. All adverse events reported will be included in the summaries and analyses.

An overall summary of adverse events is presented in [Table 47](#).

Adverse events occurring in 5% of subjects in any vaccination group will be presented in [Table 48](#).

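### Table 85, the all-dose unsolicited-AE incidence table, omits a non-serious AE with onset on Days 86-169 if dose 4 is then withheld, but counts it if dose 4 is given

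*SAP*

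**What the plan says.** The primary outcome in Protocol 3.2.1, repeated in SAP 3.2.1, is "Occurrence of unsolicited Adverse Events (AEs) through 28 days post last vaccination". Protocol 11.4.2 promises exact 95% confidence intervals for AEs in aggregate and by MedDRA category.

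In the SAP the all-dose table with those intervals is Table 85 (Appendix 1, 14.3.1.2), titled to run "Through 28 Days Post-Final Dose Received". It takes the format of Table 83, whose footnote includes AEs reported "post-dose 3 and prior to dose 4, or through 28 days post dose 3 if dose 4 not received".

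The SAP text describes something wider. Section 9.3 says: "All adverse events reported will be included in the summaries and analyses". Section 9.3.2 says: "Incidence and 95% CI of unsolicited adverse events after each dose and any time during the study will be summarized in" Tables 81 to 85. Appendix 4 labels Table 85 as post any dose. The Any Time cells of Tables 87 and 91-96 are defined as AEs reported after dose 1, with no 28-day limit in that definition.

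Protocol 5.4.3 lets a non-serious event stop the next dose. Its grounds include a Grade 3 AE that begins more than 7 days after a dose and is still ongoing at the next vaccination, a new illness that meets an exclusion criterion, and signs or symptoms that would confound reactogenicity. AEs in the long interval before dose 4 are collected. Protocol 7.6 says "All AEs will be collected and recorded on the appropriate data collection form at day 141", and Section 7.3 collects them at the Day 169 vaccination visit.

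**The concern.** Whether an AE between Day 86 and Day 169 enters Table 85 depends on something decided afterwards, namely whether dose 4 is given. Because that decision can rest on the AE itself, the event can close its own reporting window retroactively, after it has been recorded. This is outcome-dependent truncation in an estimate of a primary safety outcome. It works in one direction only, since the rule can remove events but never add them. It also leaves the SAP with two totals for one quantity, and for all-causality AEs the total with confidence intervals is the shorter one.

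**Working it through.** **The plan's own figure.** The only computed figures are in Protocol Table 10 (SAP Table 3): the probability of seeing at least one event, 1 - (1 - p)^N. For N = 10 and p = 10% this is 1 - 0.9^10 = 65.1%, as printed. All 18 entries reproduce to rounding and are not in dispute.

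**Window arithmetic.** Vaccination days are 1, 29, 57 and 169 (SAP 4.3.5). If a dose is the last one received, the last day counted is the dose day + 28.

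| Last dose received | Day | Window ends | Next scheduled dose | Days left out |
|---|---|---|---|---|
| 1 | 1 | 29 | 29 | 0 |
| 2 | 29 | 57 | 57 | 0 |
| 3 | 57 | 85 | 169 | 169 - 85 = 84 |
| 4 | 169 | 197 | none | none |

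So the problem is confined, on the nominal schedule, to the interval between doses 3 and 4. It covers 84 of the 169 - 57 = 112 days in that interval (75%). With every visit at its latest allowed day, dose 3 falls on Day 29 + 2 + 28 + 2 = 61, its window ends on Day 89, and dose 4 can fall as late as Day 61 + 112 + 5 = 178.

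**The same event under both outcomes.** Take a non-serious AE with onset on Day 120, recorded at the Day 141 visit.
- Dose 4 given: Table 85 runs to Day 197 and the AE counts. It also counts in Table 83, being after dose 3 and before dose 4.
- Dose 4 withheld: Table 85 ends on Day 85 and the AE does not count. It also leaves Table 83.

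**Effect on a displayed cell.** The Table 83 format shows each vaccine cohort separately, with 9 randomized + 1 sentinel = 10 subjects. Clopper-Pearson limits:
- one such subject counted: 1/10 = 10%, 95% CI 0.3-44.5%;
- that subject omitted: 0/10 = 0%, upper limit 1 - 0.025^(1/10) = 30.8%.

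Subjects are counted once (SAP 9.3). The subject therefore leaves a row only if no other AE in that row falls inside the window.

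**Effect on detection.** Suppose the true rate of AEs in the gap is p = 10%, and a share q of subjects with such an AE have dose 4 withheld because of it. Both values are assumptions. The chance that Table 85 shows at least one such AE among 10 subjects is 1 - (1 - p(1 - q))^10:
- q = 0: 65.1%
- q = 0.25: 54.1%
- q = 0.5: 40.1%
- q = 1: 0%

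**The case against.** The strongest defence is that Table 85 applies the protocol's primary outcome literally: 28 days after the last vaccination, where the last vaccination is the last one received. On this view, running the window to the date a dose is cancelled redefines the outcome, and sets an end date that the AE itself determines. Part of this stands. The 28-day limit comes from the protocol, so this is not purely a SAP error, and the remedy needs protocol wording too. But for a subject still on schedule at Day 120, the protocol does not say that dose 3 is already the last vaccination, and the SAP's own Sections 9.3 and 9.3.2 promise wider coverage. An end date at cancellation still varies between subjects, but it no longer removes the event that caused the cancellation.

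The second defence is that the event remains visible, and this also stands. It stays in the Any Time cells of Tables 87 and 91-96 and in Listing 11. If Grade 2-3 it is in Table 105, which shows the action taken with study treatment. Listing 1 gives the reason for stopping treatment. Tables 47 and 48 give subject counts and percentages with no stated 28-day limit. The trial tests no hypothesis, and the halting rules in Protocol 9.5.2 do not use Table 85. None of this corrects the confidence intervals in Table 85.

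A reader might infer more than the documents support:
- That every AE which stops vaccination is removed. Only non-serious AEs with onset on Days 86-169 are; those with onset by Day 85 still count, and SAEs are followed for about 6 months.
- That Table 101 (related AEs) is truncated as well. Its title says Any Time. The doubt is only whether it inherits the Table 83 footnote with the format.
- That all dose-3 displays are affected. The post-dose-3 blocks of Tables 91-96 carry no such footnote.
- That the trial loses 84/197 = 43% of its AE follow-up. That share applies only to a subject whose dose 4 is withheld; for the rest it is zero.
- That a pooled vaccine estimate such as 0/40 would be reported. The Table 85 format has no such column.

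**Conclusion.** The point holds for Table 85 and for the dose-3 tables that use the Table 83 footnote. For a subject whose dose 4 is withheld, they omit a non-serious AE arising in the 84 days after about Day 85, including one that caused the withholding, and they count the same AE if dose 4 is given. The bias in incidence and in its upper limit is downward. One affected subject in a cohort of 10 means 0/10 (95% CI 0-30.8%) in place of 1/10 (0.3-44.5%). How often this happens cannot be derived from the documents; if no dose 4 is withheld after such an AE, the effect is nil. The result assumes the nominal schedule and a literal reading of the title and footnote.

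The inconsistency does not depend on frequency. If Table 101 follows its title, a related Day-120 AE that stops dose 4 appears there but not in Table 85, so related AEs could outnumber all AEs. If Table 101 follows the Table 83 footnote, its title is wrong. Table 87 likewise carries a general 28-day footnote that conflicts with its own Any Time definition.

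**What to change.** In Table 85, count every reported unsolicited AE from first vaccination through the later of (a) 28 days after the last dose received and (b) the date the next scheduled dose was given or cancelled, no later than the end of that dose's window. Retitle the table to match SAP 9.3.2. Change the Table 83 footnote ("or through 28 days post dose 3 if dose 4 not received") in the same way. State that Table 101 follows its Any Time title, not an inherited footnote.

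In Protocol 3.2.1 and 11.4.2, clarify that AEs arising before a dose that is still scheduled fall within the reporting window. Reconcile Protocol 7.8 and 7.9 with this: at early-termination and unscheduled visits they limit recording to SAEs once 28 days have passed since the last vaccination. The data therefore exist from the scheduled Day 141 and Day 169 visits, but not necessarily from those other visits.

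The cost is a few lines of SAP wording and a short clarification to the protocol's statement of a primary outcome, with no change to procedures at scheduled visits. Reported incidence may be slightly less favourable. The change should be made before database lock.
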